**17) Provisions to Protect the Privacy Interests of Subjects**

The confidentiality practices described above will be conducted to protect the privacy interest of subjects. Any persons collecting or assessing participant data will have completed CITI certifications and will be included on the IRB protocol.

**18) Consent Process**

When the family arrives for the session, a trained member of the research team will give the parents an overview of the entire study, as well as detailed descriptions of what the visit will entail, and will answer any questions. Parents will provide consent in order for their children to participate.

Title:

Screening for Autism Spectrum Disorders Using Auditory Brainstem Responses

Number: NCT03971578

Date: May 30, 2019

Project Funded by NIH NIDCD SBIR Grant R43DC018430-01 to Intelligent Hearing Systems Corp.

Grant Title:

Screening Device for Autism Spectrum Disorders using High Stimulation Rate ABR with Continuous Loop Averaging Deconvolution

Statistical Analysis Plan

Hypothesis: The detection of neurological anomalies can be accentuated by increasing the physiological demand on neural pathways by increasing the stimulation rate (Fujikawa-Brooks et al., 2010) and therefore increasing the specificity and sensitivity of ABR testing for ASD screening.

Rationale: The purpose of this experiment is to demonstrate that higher stimulation rates, achieved using the CLAD technique (Delgado and Ozdamar, 2004), will show differences in ABRs between age-matched populations of children with and without ASD. Although the increase in rate will also increase peak latency and decrease amplitudes, the ASD population is expected to show a greater latency shift effect and increase the specificity and sensitivity of ABR testing for ASD screening. Previously, Fujikawa-Brooks et al. (2010) used a maximum rate of 61/sec and showed a significant rate effect. Because of the time constraints of a Phase I feasibility study, testing of the target population, newborns, is not possible because a confirmed ASD diagnosis will not be available for several years. The researchers recognize that there are age related differences in ABR latencies; however, these have been well documented in a normal population. The use of an age-matched control group will provide a comparison to control for normal developmental changes in ABR latencies.

Factor: Click stimulation rate (five levels): 19, 39, 61, 120, and 250 per second. The three lower rate levels were selected to replicate previous research. The upper levels were selected to obtain ABRs with discernible peaks while challenging the neural transmission of the auditory system.

Dependent Variables: Absolute peak latencies and amplitudes, and right-left ear differences of both.

Analysis: Analysis of variance and t-tests will be conducted to determine rate effects. Sensitivity and specificity measures will also be conducted for each rate at various

References:

Delgado, R.E., Özdamar, Ö. (2004). Deconvolution of evoked responses obtained at high stimulus rates, *Journal of the Acoustical Society of America*, 115:1242–1251.

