#### **4) Inclusion and Exclusion Criteria\***

Subjects will be children between the ages of 1.5 and 5.5 years. Our target age group is 3.5 to 4.5 years of age but younger or older children may be included as well. Parents must be able to communicate effectively in English to participate in the study.

A formal ASD diagnosis (i.e., community diagnosis or educational eligibility diagnosis) is required for children to be part of the ASD group. Children in the control group will not have a diagnosis of ASD or any other developmental disability. Control children will be age and gender matched with the ASD subjects. All children will be screened to insure that they do not have hearing problems, a history of middle ear infections, or a current ear infection. All children will be given an Otoacoustic Emissions (OAE) hearing screening test prior to ABR testing to confirm that their peripheral auditory system is normal.

Exclusion criteria for all subjects include: hearing problems, history of middle ear infections or current ear infection, and other abnormalities or impairments that could impact neurological functioning such as seizures, comorbid syndromes or diseases, sensory disorders, craniofacial abnormalities, other developmental or physical disabilities, or having a sibling with ASD or another developmental disability.

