**7) Data Management\***

Paper forms will be used to collect consent and demographic/family history information as well as for the ASRS and ASQ assessments. Paper forms will be scanned and stored on a secure, encrypted cloud-based system (i.e., Box) and the forms will be physically stored in a locked file cabinet.

A unique subject identifier will be assigned and used for all OAE and ABR data acquisition. OAE and ABR data will be recorded on the data acquisition system, stored electronically identified by subject number only, and backed up daily to a secure computer at the University of Miami. A deidentified database (records will be identified by subject numbers only, names will not be included) containing all study data will be created and will be accessible only to authorized study personnel. Identifying information will not be included in the analyses nor released to non-study personnel. Deidentified raw OAE and ABR data will be transferred using a secured Box account to [name] at Intelligent Hearing Systems for review to assure that the data meet the required quality for the study.

Data analysis plan:

The following statistical analyses will be performed:

- 1) Analysis of variance and t-tests will be conducted to determine if there are significant differences between the ASD and control groups, sex and ear on ABR peak latency and amplitude.
- 2) Sensitivity and specificity measures will also be conducted using Receiver Operating Characteristic (ROC) curves and d-prime measures. The optimal stimulation rate for ASD detection will be determined using these measures.

Factor: Click stimulation rate (five levels): 19, 39, 61, 120, and 250 per second. The three lower rate levels were selected to replicate previous research. The upper levels were selected to obtain ABRs with discernible peaks while challenging the neural transmission of the auditory system.

Dependent Variables: Absolute peak latencies and amplitudes.

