**15) Local Number of Subjects**

100 children 1.5-5.5 years of age will be recruited to participate in the study, including 50 children with ASD and 50 age and gender-matched controls. Additional subjects will be recruited as needed to achieve a complete age and gender matched control group and to accommodate for subjects who did not fully complete the session.

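### The SAP recognises an age effect on ABR latency but the listed analyses do not use age; an age covariate is a low-priority gain in precision, and a safeguard if matching proves loose

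*SAP*

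**What the plan says.** The SAP (Rationale) concedes the age effect: "The researchers recognize that there are age related differences in ABR latencies". Its answer is the design: "The use of an age-matched control group will provide a comparison to control for normal developmental changes in ABR latencies". Protocol section 4 admits children aged 1.5 to 5.5 years and treats the middle of that range as a preference only: "Our target age group is 3.5 to 4.5 years of age but younger or older children may be included as well". The same section states: "Control children will be age and gender matched with the ASD subjects". Section 15 plans 50 children per group and adds: "Additional subjects will be recruited as needed to achieve a complete age and gender matched control group".

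The analysis texts are short. In Protocol section 7, item 1 of the data analysis plan calls for ANOVA and t-tests for "significant differences between the ASD and control groups, sex and ear on ABR peak latency and amplitude", and click rate is listed below it as a five-level factor. Item 2 plans ROC curves and d-prime, with this purpose: "The optimal stimulation rate for ASD detection will be determined using these measures". The SAP's Analysis paragraph says "Analysis of variance and t-tests will be conducted to determine rate effects", and its next sentence breaks off in the text available.

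Neither text names age, an age stratum or the matched pair. The documents do not say whether matching is individual or by frequency, how close in age a match must be, or whether the t-tests are paired.

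**The concern.** Matching balances age between groups, but it does not by itself take age out of the error term. If latency changes with age across a four-year range and the test is unpaired, the age-related spread stays in the residual and the interval for the group difference is wider than it need be. Absolute peak latency is a listed dependent variable, and the 50-per-group sample has no stated power basis, so precision that costs almost nothing is worth having.

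There is a second stake. Matching removes age confounding only as far as it is achieved. With no stated caliper, a systematic age difference between groups is possible, and no listed analysis would correct for it.

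**Working it through.** **No plan figure to reproduce.** The documents give no age slope, latency SD, effect size, alpha or power. For orientation only: with 50 per group and an assumed two-sided 5% level, 80% power needs a difference of (1.96 + 0.84) × sqrt(2/50) = 0.56 SD.

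**Inputs.** From the documents: 50 + 50 children (Protocol section 15), ages 1.5-5.5 with a 3.5-4.5 target (section 4). Assumed: one latency value per child; a linear age slope common to both groups; residual SD of 1; R² = 0 to 0.4, the share of within-group latency variance due to age when ages are even over 1.5-5.5; two-sided 5% level.

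**Slope.** Ages even over four years have variance 4²/12 = 1.333, so b = sqrt(R²/(1−R²)/1.333). This gives 0.29 residual SD per year at R² = 0.1 and 0.71 at R² = 0.4. The slope is then held fixed while the age spread changes.

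**Unpaired test against age-adjusted.** The excess interval width is sqrt(1 + b² × age variance) − 1. At R² = 0.4 with even ages it is sqrt(1 + 0.5 × 1.333) − 1 = 29.1%.

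| Age spread (variance) | R² 0.1 | 0.2 | 0.3 | 0.4 |
|---|---|---|---|---|
| Even over 1.5-5.5 (1.333) | 5.4% | 11.8% | 19.5% | 29.1% |
| 70% in 3.5-4.5, rest even outside (0.643) | 2.6% | 5.9% | 9.9% | 15.0% |
| All in 3.5-4.5 (0.083) | 0.3% | 0.8% | 1.3% | 2.1% |

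Simulation with exactly matched pairs (20,000 replicates) agrees to within 0.1 point. Under frequency matching the even-age row becomes 4.9%, 11.3%, 19.0% and 28.5%. At R² = 0 the covariate widens intervals by 0-0.5%.

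**Paired test against age-adjusted.** Simulated intervals are about 1% wider with exact matches (49 degrees of freedom for 50 pairs, against 97) and 1.1-2.0% wider if pair members differ by up to six months.

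**Type I error, ages balanced.** An unpaired test is conservative under exact matching: with even ages the simulated level is 3.8%, 2.8%, 2.1% and 1.2% at R² 0.1 to 0.4. Under frequency matching it stays at 4.8-5.2%.

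**Type I error, systematic gap of 0.5 year (assumed), even ages.** Bias is 0.5b, or 0.144 SD at R² = 0.1 and 0.354 SD at R² = 0.4. The true standard error is sqrt(2/50) = 0.2.
- Paired: bias/SE = 0.72 and 1.77, giving about 11% and 42% (simulated 11% and 41%).
- Unpaired: the critical difference is 1.96 × 0.2 × 1.054 = 0.413 and 1.96 × 0.2 × 1.291 = 0.506. The upper tail starts at z = (0.413 − 0.144)/0.2 = 1.34 and (0.506 − 0.354)/0.2 = 0.76, giving about 9% and 22%. A separate simulation gave 10% and 26%.
- Age-adjusted: about 5%.

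**Pair term and sex.** Pairs are gender-matched, so sex is constant within a pair. Fifty pair indicators plus group have rank 51, and adding sex leaves the rank at 51. A fixed pair term therefore absorbs the sex comparison planned in Protocol section 7.

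**Where age cancels.** An age effect common to both ears drops out of a right-left difference, and one common to all rates drops out of a child's latency shift with rate.

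**ROC.** A pooled AUC of 0.70 means d = 1.414 × 0.524 = 0.742. At a given age, d is larger by the factor sqrt(1 + b² × variance). The age-specific AUC is then 0.710-0.751 with even ages and 0.701-0.704 if all children are 3.5-4.5, for R² 0.1-0.4. The sampling SD of an AUC with 50 + 50 children is about 0.04-0.05 either way.

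**The case against.** The strongest reply is that age is already handled by design and the gain may be nothing. It depends on four things the documents do not give: the age slope, the achieved age spread, the type of matching, and whether tests are paired. The sentence recognising age differences follows directly on the remark that newborns cannot be studied, so it may be aimed mainly at the use of older children. The SAP's central expectation is a larger latency shift with rate in ASD, where a common age effect cancels. All of this stands, and it is why the point is low priority. It does not remove the point: the next SAP sentence speaks of developmental change in latency within the comparison itself, and absolute latency is a listed outcome.

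Four stronger readings are tempting and not supported.
- A reader might infer that leaving age out biases the comparison or inflates false positives. If ages balance it does neither; the inflation shown above needs a systematic gap, which is assumed.
- A reader might infer that the plan certainly ignores age in analysis. The SAP sentence is cut off, and the t-tests may be paired.
- A reader might infer that pairing is the natural remedy. It recovers nearly all the precision, but it absorbs sex, loses a pair when one child's peak is unreadable, and leaves any age gap uncorrected.
- A reader might infer that the wrong stimulation rate would be chosen. Nothing in the documents shows that age adjustment would change the ranking of rates.

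**Conclusion.** The point holds as an optional improvement (could change). Apart from the matched design, no analysis text available uses age or the pair, and the evidence for this is mainly Protocol section 7. The benefit for absolute peak latency runs from nil to moderate against unpaired tests and is close to nil against tests paired on close matches. These sizes rest on an assumed R² of 0-0.4, a linear slope common to both groups, and assumed age spreads. Protection of the type I error is an added benefit only if matching leaves a systematic gap.

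Little or no gain is expected for right-left differences or rate shifts within a child. None is claimed for amplitudes, since the documents acknowledge an age effect for latencies only. An age-adjusted ROC or d-prime describes discrimination at a given age; that is a different quantity from the pooled one, not a more precise version of it.

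**What to change.** For absolute peak latencies, add continuous age as a covariate to the ANOVA that compares groups, keeping group, sex, ear and rate. Use that age-adjusted comparison in place of simple unpaired t-tests. Do not make a fixed pair term or a simple paired test the main model.

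State whether matching is individual or by frequency and how close in age it must be, and report the achieved age distribution in each group so that readers can see whether the adjustment matters. If wished, show an age-adjusted ROC and d-prime beside the pooled ones, labelled as a different quantity.

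The cost is a few lines of SAP text and one degree of freedom. No new data are needed, because age is already required for eligibility and matching.

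### The optimal click rate is to be chosen from ROC and d-prime with no interval or inferential comparison between rates, and the group-by-rate interaction is not named as the test of the greater-latency-shift claim

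*SAP*

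**What the plan says.** The SAP makes two linked claims. Its Rationale says "the ASD population is expected to show a greater latency shift effect" as the rate rises. Its Hypothesis ends with the consequence for screening: "therefore increasing the specificity and sensitivity of ABR testing for ASD screening". The Rationale also expects rate to act on everyone: "Although the increase in rate will also increase peak latency and decrease amplitudes".

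The stated analyses are these:

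- **SAP, Analysis:** "Analysis of variance and t-tests will be conducted to determine rate effects". The next sentence, "Sensitivity and specificity measures will also be conducted for each rate at various", breaks off in the text available, so nothing is inferred from what may have followed.
- **Protocol section 7, data analysis plan, item 1:** ANOVA and t-tests for "significant differences between the ASD and control groups, sex and ear on ABR peak latency and amplitude".
- **Protocol section 7, item 2:** sensitivity and specificity from ROC curves and d-prime, with the best rate for detecting ASD determined from those measures. This item is complete. It gives no interval and no test between rates.

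Both documents list click rate as a factor with five levels (19, 39, 61, 120 and 250 per second). The SAP's outcome line is "Dependent Variables: Absolute peak latencies and amplitudes, and right-left ear differences of both"; no single peak is marked as primary. Protocol section 2 makes finding the rate for newborn screening a purpose of the recordings.

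**The concern.** The greater-shift claim is a statement about group by rate: latency rises faster with rate in ASD children than in controls. The accuracy claim is a statement about differences in diagnostic accuracy between rates. The named tests concern rate in one document and group, sex and ear in the other, and the rate is picked by ranking accuracy estimates.

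Two misreadings are then open. A rate effect, which the SAP expects in all children, or a plain group effect could be reported as support when both groups slow equally. And whichever rate happens to have the highest AUC could be carried forward as the best one when the ranking is chance.

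**Working it through.** **1. Claims against stated analyses**

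| Claim | Quantity that bears on it | What the available text states |
|---|---|---|
| Rate delays the ABR in everyone (SAP, Rationale) | Rate main effect | ANOVA and t-tests for rate (SAP) |
| Delay grows more in ASD (SAP, Rationale) | Group × rate interaction | Not named; possible within an ANOVA holding both factors |
| Accuracy rises with rate (SAP, Hypothesis) | Between-rate difference in AUC | Accuracy per rate (SAP, text breaks off); ROC and d-prime (protocol item 2) |
| One rate is best (protocol sections 2 and 7) | The same difference | Ranking on ROC and d-prime |

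**2. Inputs.** From the documents: 50 + 50 = 100 children (protocol section 15) and five rates. The documents give no SD, within-child correlation, effect size or alpha, so there is no stated figure to reproduce. Everything below is illustrative: normal latencies, two-sided alpha 0.05, a range of correlations.

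**3. Ranking when no rate is better.** Put the same gap d = 0.4 SD at every rate. AUC = Φ(d/√2) = Φ(0.283) = 0.61 at all five. If the rates are equally correlated, symmetry gives 2/5 = 40% for 120/s or 250/s ranking top and 4/5 = 80% for any rate above 19/s. Simulation (50 per group, unit SD, 6,000 draws per pattern):

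| Correlation between rates | 120 or 250/s top | Any rate above 19/s top | Mean AUC gain over 19/s when 120 or 250/s is top | Group main effect p<0.05 |
|---|---|---|---|---|
| Equal 0.5 | 40.6% | 80.1% | 0.060 | 72.2% |
| Equal 0.7 | 40.1% | 79.9% | 0.047 | 62.4% |
| Equal 0.8 | 39.2% | 80.0% | 0.038 | 59.1% |
| AR(1) 0.8 | 41.7% | 74.8% | 0.061 | 64.5% |
| AR(1) 0.9 | 41.8% | 73.8% | 0.045 | 57.5% |
| Three low rates 0.9, other pairs 0.6 | 53.1% | 84.5% | 0.053 | 63.1% |

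Repeat runs put the first result column between 38% and about 55%.

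**4. Ranking when one rate is better.** With true AUC 0.75 at one rate and 0.70 at the other four, the highest observed AUC identifies the right rate in 54, 61, 72 or 93% of trials at correlation ρ = 0.3, 0.5, 0.7 or 0.9.

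**5. A rate main effect is no substitute.** Take a 0.4 SD shift that is identical in both groups. The SE of the mean within-child shift is √(2(1−ρ))/√100. At ρ = 0.3 this is 1.183/10 = 0.118, and power is Φ(0.4/0.118 − 1.96) ≈ 92%; at ρ = 0.9 it exceeds 99%. The result says nothing about ASD.

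**6. What paired AUC differences would do.** There are four comparisons with 19/s. Taking Bonferroni as one example, each interval is at 1 − 0.05/4 = 98.75% (z = 2.498). In the step 3 scenario at least one higher rate is wrongly called better in 1.6–2.3% of trials (5.9–7.9% unadjusted). The half-width for 250/s minus 19/s is 0.095–0.156 (0.07–0.12 unadjusted). If the gap truly rises from 0.4 to 1.0 SD (AUC 0.61 to 0.76), the adjusted rule succeeds in 53–96% of trials; from 0.4 to 0.8 SD, in 23–62%.

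**7. What the interaction can and cannot show.** With equal spread at all rates it rejects in 4.2–5.3% of step 3 trials. Now keep the standardized gap at 0.4, so AUC stays 0.61, but let the SD at 250/s be k times that at 19/s. The raw difference in shift is 0.4(k − 1), and the SD of the within-child shift is √(1 + k² − 2ρk). Its standard error between groups of 50 is that SD × √(2/50) = SD × 0.2.

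- k = 1.5, ρ = 0.5: 0.2/(0.2 × 1.323) = 0.756, rejection ≈ 12%. At ρ = 0.8: 0.2/(0.2 × 0.922) = 1.085, ≈ 19%.
- k = 2, ρ = 0.5: 0.4/(0.2 × 1.732) = 1.155, ≈ 21%. At ρ = 0.8: 0.4/(0.2 × 1.342) = 1.491, ≈ 32%.

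Simulation of the shift test gives about 11–32% over these settings, while the Bonferroni AUC rule stays near 2%.

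**The case against.** Several counter-arguments carry weight.

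- **The interaction may already be intended.** Rate is a listed factor, protocol section 5 uses the rates to compare ASD with control children, and an ANOVA with both factors ordinarily includes the interaction. The SAP's analysis text also breaks off. A reader might infer that the plan omits the interaction or runs the wrong test; the documents do not support that. What stands is under-specification.
- **Rates are compared.** A reader might infer that the protocol compares no rates at all. It does: choosing from ROC and d-prime is a descriptive comparison. Only the interval and the inferential comparison are absent.
- **The interaction does not test accuracy.** This stands in full (step 7). A significant interaction must not be offered as proof that sensitivity and specificity improve.
- **The percentages are largely arithmetic.** About 40% is two chances in five, and when all AUCs are equal, choosing any rate loses no true accuracy. Agreed: the harm in that case is an optimistic gain and unearned support for the hypothesis. Step 4 shows that a wrong choice is also possible when the rates differ.
- **The stage limits the harm.** The SAP describes the constraint itself: "Because of the time constraints of a Phase I feasibility study", newborns are not tested. Protocol section 3 says that a broader study of well babies is needed for new accuracy measures. It would go too far to say that a screening rate will be fixed from these data alone.
- **Strict adjustment may be too much for feasibility work, and the simulation ignores matching and the two ears.** Both are fair. The multiplicity method and the peak should be the sponsor's choice.

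**Conclusion.** The point holds in limited form. The secure part is protocol section 7, item 2: the rate is determined from accuracy estimates with nothing to separate a real difference from chance. With 50 per group and an assumed constant gap of 0.4 SD, one of the two fastest rates ranks top in about 40 to 55% of trials, with an apparent AUC gain of 0.04 to 0.06 over 19/s that is not real. The second part is a gap in specification: the available text does not name the group × rate term as the test of the greater-shift claim, or one peak on which to test it.

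These sizes rest on assumed effect sizes, normality, equal spread across rates and the correlation patterns shown; the documents supply none of them. The fault in specification does not depend on them. It is worth correcting before analysis, with moderate confidence, and it does not undermine the study's design.

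**What to change.** Amend SAP Analysis and protocol section 7 in the same terms.

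1. **Accuracy claim and rate choice.** Report the AUC at each rate with a 95% CI, and the paired AUC difference from 19/s for each of 39, 61, 120 and 250/s, by DeLong's method or a bootstrap that resamples whole children. State the multiplicity approach. Describe a higher rate as better than 19/s only if its interval lies wholly above 0; otherwise label the optimal rate exploratory.
2. **Greater-latency-shift claim.** Name the group × rate interaction, from a repeated-measures ANOVA or mixed model, on the latency of one primary peak named in advance by the sponsor (the protocol's background draws attention to wave V). Report the group difference in the 19/s-to-250/s shift with a 95% CI. State that this result is not evidence of better accuracy.

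The cost is wording in two documents and a little more analysis of recordings already planned, with no extra children or visits. The downside is a commitment to one peak and fairly wide intervals. If the accentuation is modest, the optimal rate may well remain exploratory, which suits a Phase I feasibility study.
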